6.3 Exit criteria

Subjects will be required to exit the study if either of the following events occurs:

- Subject completes the first 6 weeks of the Treatment Period (after randomization) and experiences ≥ 2 PGTC seizures during that time
- Subject experiences a second PGTC seizure after the first 6 weeks of the Treatment Period
- The 125th event occurs in the study

Once the subject has experienced 2 PGTC seizures, the site should contact the Medical Monitor to confirm whether the subject has met the exit criteria. If the exit criteria are met, sites will be advised to have subjects return for their ET Visit within **1 week** of the subject's second seizure, with the following exception: if the 2 PGTC seizures occur during the first 6 weeks of the Treatment Period (after randomization), the subject should continue the Titration Period visits and wait for the end of the first 6 weeks of the Treatment Period to complete the ET Visit.

6.4 Withdrawal criteria

Subjects are free to withdraw from the study at any time, without prejudice to their continued care.

Subjects **must** be withdrawn from the study if any of the following events occurs:

- The subject is unable to attain at least the minimum Maintenance Period target dose (Table 7-3).
- The subject requires a subsequent dose increase after dose reduction during the Maintenance Period or the subject requires more than 1 dose reduction during the Maintenance Period.
- Subject develops a second- or third-degree AV block.
- The subject becomes pregnant, as evidenced by a positive pregnancy test.
- The sponsor or a regulatory agency requests withdrawal of the subject.
- The subject is unwilling or unable to continue and withdraws consent.
- In the case of liver function test (LFT) results of transaminases (AST and/or ALT) $\geq 3 \times \text{ULN}$ to $< 5 \times \text{ULN}$ and total bilirubin $\geq 2 \times \text{ULN}$ or transaminases (AST and/or ALT) $\geq 5 \times \text{ULN}$, LCM must be immediately discontinued and the subject withdrawn from the study. The LFTs will be repeated as soon as possible, and in no case more than 1 week later.
- Subject ≥ 6 years of age has actual suicidal ideation as indicated by a positive response ("Yes") to either Question 4 or Question 5 of the "Since Last Visit" version of the C-SSRS. The subject should be referred immediately to a Mental Healthcare Professional and must be withdrawn from the study.

Subjects **may** be withdrawn from the study if any of the following events occur:

- The subject requires a medication that is not permitted.
- The subject requires a modification to concomitant AED dose(s) during the study (see Section 7.8).
- The subject is unable to manage the completion of the diary, demonstrates a questionable diary, or is noncompliant with the study procedures or medications in the opinion of the investigator.
- An episode of status epilepticus, a prolongation of seizure duration, a worsening of seizure frequency, or emergence of a new seizure type considered by the investigator to require intervention.
- Subject develops a clinically relevant change in medical condition (or ECG or laboratory parameter) as determined by the investigator, and the investigator feels it is in the interest of the subject to withdraw.
- Subject develops an intolerable AE during the course of the study.
- Discontinuation criteria for potential drug-induced liver injury (PDILI) are described in Section 6.4.1.

Investigators should attempt to obtain information on subjects, in the case of withdrawal. For subjects considered as lost to follow up, the investigator should make an effort (at least 1 phone call and 1 written message to the subject), and document his/her effort (date and summary of the phone call and copy of the written message in the source documents), to complete the final evaluation. All results of these evaluations and observations, together with a narrative description of the reason(s) for removing the subject, must be recorded in the source documents. The electronic Case Report form (eCRF) must document the primary reason for withdrawal.

Investigators should contact the Medical Monitor whenever possible to discuss the withdrawal of a subject in advance.

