6.4.1 Potential drug-induced liver injury IMP discontinuation criteria

Subjects with PDILI must be assessed to determine if IMP must be immediately and permanently discontinued. In addition, all concomitant medications and herbal supplements that are not medically necessary should also be discontinued.

The PDILI criteria below require immediate and permanent discontinuation of IMP:

- ALT or AST $\geq 5xULN$
- ALT or AST $\geq 3xULN$ and coexisting total bilirubin $\geq 2xULN$
- Subjects with ALT or AST $\geq 3xULN$ who exhibit temporally associated symptoms of hepatitis or hypersensitivity. Hepatitis symptoms include fatigue, nausea, vomiting, right upper quadrant pain or tenderness. Hypersensitivity symptoms include fever (without clear alternative cause), rash, or eosinophilia (ie, $>5\%$).

The PDILI criterion below allows for subjects to continue on IMP at the discretion of the investigator.

- Subjects with ALT or AST $\geq 3 \times$ ULN (and $\geq 2 \times$ Baseline) and $< 5 \times$ ULN, total bilirubin $< 2 \times$ ULN, and no eosinophilia (ie, $\leq 5\%$), with no fever, rash, or symptoms of hepatitis (eg, fatigue, nausea, vomiting, right upper quadrant pain or tenderness).

Evaluation of PDILI must be initiated as described in Section 10.2.1. If subjects are unable to comply with the applicable monitoring schedule, IMP must be discontinued immediately.

Investigators should attempt to obtain information on subjects in the case of IMP discontinuation to complete the final evaluation. Subjects with PDILI should not be withdrawn from the study until investigation and monitoring are complete. All results of these evaluations and observations, as well as the reason(s) for IMP discontinuation and subject withdrawal (if applicable), must be recorded in the source documents. The eCRF must document the primary reason for IMP discontinuation.

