When IMP is stopped due to PDILI (as described in Section 6.4.1), IMP must be permanently discontinued. Rechallenge with a substance potentially causing drug-induced liver injury is dangerous, may be fatal, and must not occur.

The table below summarizes the approach to investigate PDILI.

This document cannot be used to support any marketing authorization application and any extensions or variations thereof.

REDACTED COPY

Table 10-3: Required investigations and follow up for PDILI

| Laboratory value | | Immediate | | | Follow up | |
|--------------------------------------|---------------------|--|---|---|---|---|
| ALT or AST | Total bilirubin | Symptoms ^a of hepatitis or hypersensitivity | Consultation requirements | Actions | Testing | Evaluation |
| ≥3xULN | ≥2xULN ^b | NA | Hepatology consult. ^c Medical Monitor must be notified within 24 hours (eg, by laboratory alert) and subject discussed with Medical Monitor ASAP. | Immediate, permanent IMP discontinuation. | Essential: Must have repeat liver chemistry values and additional testing completed ASAP (see Section 10.2.1.3); recommended to occur at the site with HCP. | Monitoring of liver chemistry values at least twice per week until values normalize, stabilize, or return to within Baseline values. ^d |
| ≥8xULN | NA | NA | | | | |
| ≥3xULN | NA | Yes | | | | |
| ≥3xULN (and ≥2x Baseline) and <5xULN | <2xULN | No | Discussion with Medical Monitor required if the criterion that allows for IMP continuation is met. | Further investigation of immediate IMP discontinuation not required (see Section 10.2.1.2). | Not required unless otherwise medically indicated (at discretion of investigator). | |
| ≥5xULN (and ≥2x Baseline) | <2xULN | No | Discussion with Medical Monitor required. | Immediate, permanent IMP discontinuation. | Essential: Every attempt must be made to have repeat liver chemistry values and additional testing completed within 48 hours at the site with HCP (see Section 10.2.1.3). | Monitoring of liver chemistry values at least twice per week until values normalize, stabilize, or return to within Baseline values. ^d |

ALP=alkaline phosphatase; ALT=alanine aminotransferase; ASAP=as soon as possible; AST=aspartate aminotransferase; HCP=healthcare practitioner;

IMP=investigational medicinal product; NA=not applicable; PDILI=potential drug-induced liver injury; ULN=upper limit of normal

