10.2.1.1 Consultation with Medical Monitor and local hepatologist

Potential drug-induced liver injury events require notification of the Medical Monitor within 24 hours (eg, by laboratory alert), and the subject must be discussed with the Medical Monitor as soon as possible. If required, the subject must also be discussed with the local hepatologist. The local hepatologist is the expert usually consulted by the treating physician for assessment and management of potential hepatic disease. This would usually be a hepatologist, but may be a gastroenterologist. If determined necessary, this discussion should be followed by a full hepatology assessment (see Section 10.2.1.3) and SAE report (if applicable).

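### For the same liver results, Section 6.4 withdraws the subject from the study while Section 6.4.1 holds withdrawal back until the liver work-up is finished

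*Protocol*

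**What the plan says.** Section 6.4 has two lists: events after which a subject must be withdrawn, and events after which a subject may be.

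- **Mandatory list, liver bullet.** For AST and/or ALT from 3xULN to below 5xULN with total bilirubin at least 2xULN, or AST and/or ALT at least 5xULN, "LCM must be immediately discontinued and the subject withdrawn from the study". The bullet then adds: "The LFTs will be repeated as soon as possible, and in no case more than 1 week later".
- **Optional list, last bullet.** "Discontinuation criteria for potential drug-induced liver injury (PDILI) are described in Section 6.4.1". This is the only pointer from Section 6.4 to Section 6.4.1.

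Section 6.4.1 gives three criteria for immediate and permanent discontinuation of IMP: ALT or AST at least 5xULN; at least 3xULN with total bilirubin at least 2xULN; and at least 3xULN with symptoms of hepatitis or hypersensitivity. On participation it says: "Subjects with PDILI should not be withdrawn from the study until investigation and monitoring are complete". On documentation it says that "the reason(s) for IMP discontinuation and subject withdrawal (if applicable), must be recorded in the source documents".

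For subjects whose IMP is stopped, Table 10-3 in Section 10.2.1 sets the follow-up: "Monitoring of liver chemistry values at least twice per week until values normalize, stabilize, or return to within Baseline values". A footnote allows another schedule if the investigator and the sponsor's responsible physician agree on one.

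**The concern.** A site with a subject at these thresholds finds two instructions about study participation. One is in a list headed by a must and carries no condition. The other is a should-not in the next subsection. Nothing says which governs. A site that weighs the two verbs, or reads only the mandatory list, would withdraw the subject straight away, which is the less protective course.

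The subjects concerned are those for whom the work-up matters most, because the bilirubin criterion takes in potential Hy's Law cases. At stake are continued participation during the hepatic investigation and consistent recording of disposition across sites. Efficacy is not at stake.

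**Working it through.** The plan states no figure on this point. The check compares the two sets of triggers, then the actions attached to them.

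**1. Are the triggers the same?** Let T be ALT or AST and B total bilirubin, each in multiples of ULN.

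- Section 6.4 liver bullet: {3 ≤ T < 5 and B ≥ 2} or {T ≥ 5}.
- Section 6.4.1, first two criteria: {T ≥ 5} or {T ≥ 3 and B ≥ 2}.

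The set {T ≥ 3 and B ≥ 2} splits into {3 ≤ T < 5 and B ≥ 2} and {T ≥ 5 and B ≥ 2}. The second part already lies inside {T ≥ 5}. Both sections therefore describe the same set, and every subject who meets the Section 6.4 bullet is a PDILI subject under Section 6.4.1. Of the three mandatory-stop criteria in Section 6.4.1, two are shared with the bullet. The symptomatic criterion is not.

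**2. Are the actions the same?**

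| | Section 6.4 bullet | Section 6.4.1 and Table 10-3 |
|---|---|---|
| Drug | Stop at once | Stop at once, permanently |
| Study participation | Withdraw; no deferral stated | Do not withdraw until the work-up is complete |
| Repeat liver test | As soon as possible, at most 1 week later | As soon as possible; for T ≥ 5 (and at least twice Baseline) with B < 2 and no symptoms, every attempt within 48 hours |
| Later monitoring | Not stated | At least twice weekly until resolved or stable, unless another schedule is agreed |

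The drug row agrees. The participation row conflicts. On repeat testing both sources ask for speed, but the 1-week maximum in the bullet is looser than the 48-hour target and than a twice-weekly schedule.

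**3. Is the conflict in current text?** Yes: both instructions stand in the body of the protocol. The Amendment 4 log suggests how it arose. That amendment added Section 6.4.1 and replaced a different liver bullet with the pointer, while this bullet stayed. That is background only; the finding does not depend on it.

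**4. What continues after withdrawal?**

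- Section 10.1.3 asks for an ongoing adverse event to be followed to resolution or stability even when the subject's study has ended.
- Section 10.2.1 makes every PDILI event a reportable adverse event and requires abnormal liver tests to be repeated.
- Section 10.2.1.2 requires action, testing and monitoring for all PDILI events.
- Section 10.2.1.4 continues monitoring until values normalize, stabilize or return to Baseline.

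None of these lapses on withdrawal.

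**5. Does the primary analysis change?** Section 13.3.1 censors premature discontinuations at the last dose of study drug. Both sections fix that date in the same way, so the effect is negligible.

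**The case against.** The best defence is that the two texts can be read together. In the Section 6.4 bullet, immediacy attaches to stopping the drug, and no time is set for withdrawal. Section 6.4.1 then supplies the time. Section 10.2.1 also names Section 6.4.1 as the home of the PDILI stopping criteria. This reading is available and sensible, but the reader has to supply it: the bullet does not mention Section 6.4.1, and the only pointer sits in the optional list.

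The defence is stronger on consequences, and that part stands. Besides the follow-up rules above, "Potential drug-induced liver injury events require notification of the Medical Monitor within 24 hours", and for withdrawals in general, "Investigators should contact the Medical Monitor whenever possible to discuss the withdrawal of a subject in advance".

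Three stronger readings are tempting, and the documents do not support them.

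- **That withdrawal costs a countable number of liver samples.** Any such count assumes that a site ignores Table 10-3, which withdrawal does not cancel. It must also leave out the Early Termination Visit chemistry and the footnote that permits another schedule. No sample count should be claimed.
- **That Section 6.4.1 makes withdrawal optional for these subjects because it says "the reason(s) for IMP discontinuation and subject withdrawal (if applicable), must be recorded in the source documents".** That paragraph covers all PDILI subjects, including those with the symptomatic criterion and those allowed to stay on IMP. The qualifier is needed for them and does not by itself contradict Section 6.4. The conflict rests on deferral alone.
- **That the primary result could be biased.** The drug stop and the censoring date do not depend on which instruction is followed.

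**Conclusion.** The point holds as a conflict between two current safety instructions on study participation, triggered by identical liver results, with a secondary mismatch in the tolerated delay for repeat testing. It should be corrected, because it concerns the most serious liver cases and the correction is nearly free.

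Its size is modest. It applies to any subject who reaches either shared threshold, and the protocol gives no expected number. Follow-up of the liver event is required whichever instruction a site follows, so the practical loss may be small or nil. Sample size, error rate and the primary estimate are essentially unaffected. The conclusion assumes that sites may act on the mandatory list as written, and that no instruction outside the protocol already settles which section governs.

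**What to change.** Replace the Section 6.4 liver action with wording such as: *IMP must be stopped immediately and permanently; the subject is withdrawn from the study only after PDILI investigation and monitoring are complete (Sections 6.4.1 and 10.2.1). Repeat testing and monitoring follow Table 10-3.*

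Delete the separate 1-week limit, so that one clock governs repeat testing. Twice-weekly monitoring already brings the next sample in under a week unless another schedule is agreed. Keep the existing pointer to Section 6.4.1 in the optional list, because it serves the PDILI criteria that this bullet does not cover.

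The cost is one reworded bullet, in the next amendment or a clarification letter to sites. Visits, data collection and analysis do not change.

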6.4.1 Potential drug-induced liver injury IMP discontinuation criteria

Subjects with PDILI must be assessed to determine if IMP must be immediately and permanently discontinued. In addition, all concomitant medications and herbal supplements that are not medically necessary should also be discontinued.

The PDILI criteria below require immediate and permanent discontinuation of IMP:

- ALT or AST $\geq 5xULN$
- ALT or AST $\geq 3xULN$ and coexisting total bilirubin $\geq 2xULN$
- Subjects with ALT or AST $\geq 3xULN$ who exhibit temporally associated symptoms of hepatitis or hypersensitivity. Hepatitis symptoms include fatigue, nausea, vomiting, right upper quadrant pain or tenderness. Hypersensitivity symptoms include fever (without clear alternative cause), rash, or eosinophilia (ie, $>5\%$).

The PDILI criterion below allows for subjects to continue on IMP at the discretion of the investigator.

- Subjects with ALT or AST $\geq 3 \times$ ULN (and $\geq 2 \times$ Baseline) and $< 5 \times$ ULN, total bilirubin $< 2 \times$ ULN, and no eosinophilia (ie, $\leq 5\%$), with no fever, rash, or symptoms of hepatitis (eg, fatigue, nausea, vomiting, right upper quadrant pain or tenderness).

Evaluation of PDILI must be initiated as described in Section 10.2.1. If subjects are unable to comply with the applicable monitoring schedule, IMP must be discontinued immediately.

Investigators should attempt to obtain information on subjects in the case of IMP discontinuation to complete the final evaluation. Subjects with PDILI should not be withdrawn from the study until investigation and monitoring are complete. All results of these evaluations and observations, as well as the reason(s) for IMP discontinuation and subject withdrawal (if applicable), must be recorded in the source documents. The eCRF must document the primary reason for IMP discontinuation.

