After completing ≥ 6 weeks and experiencing the second PGTC seizure during the Treatment Period or after completing the 24-week Treatment Period or if the 125th event occurs in the study (whichever comes first), eligible subjects may, at the ET Visit or Visit 10 (Week 24) respectively, choose to continue in EP0012. Subjects completing Visit 10 (Week 24) or the ET Visit must complete a 4-week blinded transition followed by a Final Clinic Visit. The Final Clinic Visit is the same as Visit 1 of EP0012 (see [Section 7.2.3](#)). During the 4-week blinded transition, subjects receiving placebo during SP0982 will have their dose titrated to LCM (see [Table 7-4](#)).

If the subject discontinues from the study at any time and is not eligible or chooses not to enter EP0012, the subject must complete the ET Visit or Visit 10 (Week 24), and an up to 4-week blinded taper followed by an End of Taper Visit. Following the End of Taper Visit, there will be a 30-day Safety Follow-up Period (see Section 7.2.4). In case the 125th event occurs in the study, the subjects discontinuing treatment will complete the ET Visit or Visit 10 (Week 24), and an up to 4-week blinded taper followed by an End of Taper Visit. However, the End of Taper Visit will be the same as Visit 1 of EP0012. The 30-day Safety Follow up Period will be done as part of EP0012, except if the subject refuses to sign the EP0012 informed consent form. If the subject signs the informed consent form for a short Safety Follow-up as part of EP0012, the 30-day Safety Follow-up will be performed as part of EP0012; otherwise, the Safety Follow-up will be performed in SP0982.

Unscheduled visits may be performed at any time after Visit 1 at the discretion of the investigator.

Schematic diagrams of the study are provided in Section 5.3.

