7.2.4 Taper Period

If the subject discontinues from the study at any time and is not eligible or chooses not to enter EP0012, the subject must complete the ET Visit or Visit 10 (Week 24) and an up to 4-week blinded taper followed by an End of Taper Visit ([Table 7-5](#)).

A slower taper is permitted if medically necessary. Whenever possible, these cases should be discussed with the Medical Monitor prior to withdrawing the subject from the study, especially in cases in which exit criteria have been met. In case of an emergency, a faster taper is permitted after discussion with the Medical Monitor, whenever possible.

Following the End of Taper Visit, there will be a 30-day Safety Follow-up Period. The Safety Follow-up Period consists of a clinic visit 2 weeks after the End of Taper Visit followed by a Safety Follow-up telephone contact 30 days after the last dose of study drug. In case the 125th event occurs in the study, the subjects discontinuing treatment will complete the ET Visit or Visit 10 (Week 24), and an up to 4-week blinded taper followed by an End of Taper Visit. However, the End of Taper Visit will be the same as Visit 1 of EP0012. The 30-day Safety Follow-up Period will be done as part of EP0012, except if the subject refuses to sign the EP0012 informed consent form. If the subject signs the informed consent form for a short Safety Follow-up as part of EP0012, the 30-day Safety Follow-up will be performed as part of EP0012; otherwise, the Safety Follow-up will be performed in SP0982.

The following schematic displays the scenario for subject dispensation:

ET=Early Termination; TC=telephone contact

Note: An End of Taper Visit will be scheduled at the end of the Taper Period (up to 4 weeks) depending on the dose level achieved; see Table 7-5. Of note, for subjects who enter the Taper Period at 2mg/kg/day (oral solution) or 100mg/day (tablets), the End of Taper Visit will take the place of the ET Visit.

Table 7-5 summarizes the Taper Period dosing for each treatment dose for subjects not entering EP0012.

Table 7-5: Taper Period dosing of LCM (or matching placebo)

| LCM (or matching placebo) dose achieved | LCM (or matching placebo) doses for the Taper Period | | | |
|---|--|------------|------------|------------|
| | Week 1 | Week 2 | Week 3 | Week 4 |
| 11 or 12mg/kg/day | 9mg/kg/day | 6mg/kg/day | 4mg/kg/day | 2mg/kg/day |
| 9 or 10mg/kg/day | 8mg/kg/day | 6mg/kg/day | 4mg/kg/day | 2mg/kg/day |

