8.2.2 Titration Period

8.2.2.1 Week 1 to Week 6

Both clinic visits and telephone contacts will be conducted during the Titration Period, beginning with a telephone contact at the end of Week 1 and continuing through clinic Visit 5 at the end of Week 6.

At each clinic visit and telephone contact, the investigator, in conjunction with the subject and/or parent(s)/legal representative(s), will decide how to proceed with study drug dosing based on tolerability (including vital signs, body weight, 12-lead ECG, and AE reporting, as applicable to the type of visit contact). If the withdrawal of study drug is required during the Titration Period, the subject will enter the blinded Taper Period (Table 7-5).

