8.2.2.1.2 Visit 3 (end of Week 2)

During Visit 3 (end of Week 2), the following assessments will be performed:

- Body weight
- Physical examination (brief)
- Neurological examination (brief)
- ECG 12-lead assessment (see Section 10.3.1)
- Vital signs (pulse rate, systolic BP, and diastolic BP, including orthostatic assessments)
- C-SSRS assessment (for subjects ≥ 6 years of age)
- Blood and urine samples for clinical laboratory assessments (includes hematology, chemistry, urinalysis, and a urine pregnancy test [for women of childbearing potential])
- Subject diary return/review
- Dispense subject diary
- Dispense study drug
- Study drug review/return
- Healthcare resource use
- Work/school days lost due to epilepsy
- Days with help from a caregiver due to epilepsy
- Socio-professional data

-
- AE reporting
 - Concomitant medications and AEDs
 - Withdrawal criteria
 - Contact IRT

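### The taper rules in Sections 8.2.2.1, 5.1 and 7.2.4 make no exception for the immediate, permanent liver stop in Section 6.4.1

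*Protocol*

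**What the plan says.** **The liver stop.** Protocol Section 6.4.1 states "The PDILI criteria below require immediate and permanent discontinuation of IMP" for three criteria: ALT or AST ≥5×ULN; ALT or AST ≥3×ULN with total bilirubin ≥2×ULN; and ALT or AST ≥3×ULN with symptoms of hepatitis or hypersensitivity. Section 10.2.1 and Table 10-3 repeat that the stop is permanent, and 10.2.1 forbids rechallenge. For the two laboratory criteria, Section 6.4 adds, under its compulsory withdrawals, "LCM must be immediately discontinued and the subject withdrawn from the study".

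**The taper in titration.** Section 8.2.2.1 says "If the withdrawal of study drug is required during the Titration Period, the subject will enter the blinded Taper Period (Table 7-5". Its span runs from the Week 1 telephone contact, "continuing through clinic Visit 5 at the end of Week 6".

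**The taper at any time.** A subject who leaves the study and does not enter EP0012 "must complete the ET Visit or Visit 10 (Week 24) and an up to 4-week blinded taper" (Section 7.2.4). Section 5.1 says the same: "must complete the ET Visit or Visit 10 (Week 24), and an up to 4-week blinded taper". The only relief is speed: "In case of an emergency, a faster taper is permitted after discussion with the Medical Monitor, whenever possible". Table 7-5 drops the taper only at 100 mg/day or ≤2 mg/kg/day.

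**Withdrawal.** Section 6.4.1 asks that subjects with potential liver injury stay in the study until investigation and monitoring are finished, and treats withdrawal as something that may or may not apply. In Section 6.4 the pointer to 6.4.1 stands in the list of optional withdrawals.

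**The concern.** A subject cannot stop the drug at once and also take stepped-down doses for one to four weeks. One rule protects a subject with suspected drug-induced liver injury, who may be a child as young as 4 years. The other is the protocol's routine exit path and is written without exceptions. The protocol does not say which prevails. A site that follows the exit path to the letter keeps giving a drug suspected of injuring the liver.

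A lesser problem sits beside this. Section 6.4 makes withdrawal compulsory for the two laboratory criteria, Section 6.4.1 defers it, and the cross-reference between the two sections is filed under optional withdrawals. The order of events (drug stop, work-up, withdrawal) is left to be inferred.

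**Working it through.** The protocol gives no figure for this, so the check sets the texts side by side and then sums Table 7-5.

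**Step 1: what triggers each taper rule.**

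- Section 8.2.2.1 is triggered by stopping study drug. A liver stop is such a stop, so all three criteria in 6.4.1 are caught.
- Sections 5.1 and 7.2.4 are triggered by leaving the study. After titration they catch directly only the subjects whom 6.4 says must be withdrawn on liver grounds, which are those meeting the two laboratory criteria. The symptomatic criterion is not in that list.

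**Step 2: whether anything exempts a liver stop.** None of the three taper sections mentions liver injury. The emergency clause in 7.2.4 shortens the taper but does not waive it. Section 6.4.1 does not mention the taper. For pregnancy, by contrast, Section 10.1.4 offers an immediate stop or a down-titration.

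**Step 3: extra drug if the taper text is followed.** Inputs are the starting doses in Table 7-1 (recommended titration) and Table 7-3 (maintenance range), and the weekly steps in Table 7-5. Extra drug = 7 days × sum of the weekly daily doses.

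| Dose at stop | Sum | Extra drug | Duration |
|---|---|---|---|
| 100 mg/day (Week 1) | none | 0 | none |
| 200 mg/day (Week 2) | 7 × 100 | 700 mg | 1 week |
| 300 mg/day (Week 3; maintenance minimum) | 7 × (200 + 100) | 2,100 mg | 2 weeks |
| 400 mg/day (Weeks 4 to 6; maintenance maximum) | 7 × (300 + 200 + 100) | 4,200 mg | 3 weeks |
| 2 mg/kg/day (Week 1) | none | 0 | none |
| 4 mg/kg/day (Week 2) | 7 × 2 | 14 mg/kg | 1 week |
| 6 mg/kg/day (Week 3; maintenance minimum, 30 to <50 kg) | 7 × (4 + 2) | 42 mg/kg | 2 weeks |
| 8 mg/kg/day (Week 4; maintenance maximum, 30 to <50 kg; minimum, <30 kg) | 7 × (6 + 4 + 2) | 84 mg/kg | 3 weeks |
| 10 mg/kg/day (Week 5, <30 kg) | 7 × (8 + 6 + 4 + 2) | 140 mg/kg | 4 weeks |
| 12 mg/kg/day (Week 6; maintenance maximum, <30 kg) | 7 × (9 + 6 + 4 + 2) | 147 mg/kg | 4 weeks |

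**Step 4: when a liver result would arise in titration.** Section 8 schedules chemistry at Visit 3 (end of Week 2) and Visit 5 (end of Week 6), and none at Visit 4. A Visit 3 result acted on at the Week 2 dose gives 700 mg or 14 mg/kg. Acted on in Week 3 it gives 2,100 mg or 42 mg/kg. At Visit 5, on the recommended dose, it gives 4,200 mg, 84 mg/kg or 147 mg/kg by weight group. Section 8.2.2.1 counts Visit 5 as the end of titration, while 8.2.3.1 lists it under Maintenance.

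**Step 5: 6.4 against 6.4.1 on withdrawal.** In 6.4 the word for immediacy attaches to the drug stop, not to the withdrawal. The two sections can therefore be read together as stopping drug now and withdrawing after the work-up. That order is not written down. The pointer under the optional list also does not fit, because two of the criteria it points to are compulsory withdrawals a few lines above.

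**The case against.** The strongest reply is that the specific rule governs. The sentence in 8.2.2.1 closes a paragraph about dosing by tolerability, and laboratory results are not among the items named there. Section 10.2.1.2 sends the liver decision to 6.4.1 and Table 10-3, neither of which includes a taper. Section 10.2.1 bans rechallenge, and 10.2.1.1 brings in the Medical Monitor within 24 hours. A careful investigator would very probably stop the drug outright. This stands, and it is why the harm is not expected. It does not remove the conflict: the 8.2.2.1 rule is unqualified and nothing states precedence.

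A second reply is that a subject already off drug enters the taper at zero, where Table 7-5 requires none. That is sensible but not written. The table is keyed to the dose achieved, and its lowest tablet row is 100 mg/day.

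The pregnancy comparison cuts both ways. It shows that the protocol can write an immediate stop. It also shows a topic-specific section overriding 7.2.4 without an exemption there.

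Three stronger readings are tempting and are not supported:

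- *That 6.4 and 6.4.1 flatly contradict each other on when to withdraw.* The joint reading in Step 5 resolves most of the timing.
- *That a symptomatic subject would be restarted on drug by a taper at later withdrawal.* A taper presupposes current dosing, and 10.2.1 already forbids restarting.
- *That the symptomatic criterion was wrongly left out of the compulsory withdrawals.* Stopping drug while staying in the study for monitoring is coherent, and 6.4.1 leaves withdrawal open. Making it compulsory would be a policy change, not a correction.

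**Conclusion.** The contradiction is in the current text and should be fixed. During titration it covers all three mandatory liver criteria, with no practical effect in Week 1, when no taper dose is due. After titration it covers the two laboratory criteria. The placing of the 6.4.1 pointer and the unstated order of drug stop, work-up and withdrawal are secondary.

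The largest possible excess is 4,200 mg over 3 weeks at 50 kg and above, 84 mg/kg over 3 weeks at 30 to <50 kg, and 147 mg/kg over 4 weeks below 30 kg. These are upper bounds. They apply to the lacosamide arm only and assume that the full taper is taken and the liver sections are disregarded. The protocol gives no frequency for these events, so expected harm cannot be put in numbers. A reader might infer that the protocol directs continued dosing after liver injury as a matter of course. It does not, because the repeated liver rule would probably prevail. Sample size, power and type I error are untouched.

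**What to change.** 1. In Sections 5.1, 7.2.4 and 8.2.2.1 add: *except subjects meeting a mandatory liver stop criterion in Section 6.4 or 6.4.1, who stop IMP at once and do not taper.* Put a matching cross-reference in 6.4.1.
2. In Section 6.4, reword the liver bullet so that the subject is *withdrawn once the investigation and monitoring in Section 6.4.1 are complete*. Move the 6.4.1 pointer out of the optional list and make it a neutral cross-reference. Leave to the sponsor whether the symptomatic criterion should also require study withdrawal.
3. For the primary analysis, state that these subjects are premature discontinuations censored at the last dose of IMP, whatever date withdrawal is recorded. Section 13.3.1 already censors premature discontinuations at last dose. Without this sentence, a subject who is off drug but not yet withdrawn and has a second PGTC seizure could meet an exit criterion (6.3) and count as a completer (5.1.2).
4. Leave the taper, including the faster emergency taper, unchanged for all other withdrawals.

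The cost is a few sentences in an amendment. No visits, tests or subjects are added: the ET Visit, the safety follow-up timed from the last dose (8.3.2.2 and 8.3.2.3) and the Table 10-3 monitoring are already required.
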